6.10 Discontinuation and Withdrawal Criteria

6.10.1 Discontinuation of Treatment

Patients may voluntarily discontinue from treatment for any reason at any time. If a patient decides to discontinue from treatment, the Investigator must make every effort to determine the primary reason for this decision. The reason for discontinuation should be recorded in the patient's chart and on the appropriate eCRF pages.

Patients who discontinue IMP treatment during the Double-Blind Treatment Period should NOT be considered withdrawn from the trial. Every effort will be made to keep patients who discontinue IMP treatment in the trial. They should return for the assessments indicated in Table 3, up to Week 53. A PK sample and an immunogenicity sample should be collected at least 5 weeks after the last dose of IMP.

If the patients fail to return for these assessments for unknown reasons, every effort (e.g., telephone, email, letter) should be made to contact them. Patients who discontinue IMP treatment during the Extension Period should be asked to complete an End-of-Treatment Visit as soon as possible after the last dose of IMP, and a Safety Follow-Up Visit at least 5 weeks after last dose of IMP.

The Investigator should discontinue a patient's IMP treatment if he/she believes that continuation would be detrimental to the patient's well-being or if the patient experiences an intercurrent illness that compromises the patient's ability to fulfil protocol requirements. The Investigator should contact the Medical Monitor before a patient is discontinued from IMP treatment.

IMP treatment must be discontinued under the following circumstances:

- Development of decreased kidney function as defined by $\text{eGFR} < 25 \text{ mL/min/1.73 m}^2$.
- Pregnancy (see [Section 7.6.1.1](#)).
- Any protocol deviation (including prohibited concomitant therapy, see [Section 6.9.3](#)) that results in a significant risk to the patient's safety or that will interfere with the assessment of the efficacy endpoints of this trial, including significant non-compliance with the trial protocol and procedures.

In addition to the general treatment discontinuation criteria, the toxicity-related criteria listed below will also require IMP treatment discontinuation. The final decision to discontinue IMP treatment is up to the judgment of the Investigator.

Hepatic-related Discontinuation Criteria

- ALT or AST levels $> 8 \times$ upper limit of normal.

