7 TRIAL ASSESSMENTS AND PROCEDURES

7.1 Trial Procedures and Flow Charts

Trial procedures and their timing for patients during the trial are summarized in [Table 3](#). Protocol waivers or exemptions are not allowed. Immediate safety concerns should be discussed with the Sponsor immediately upon occurrence or awareness to determine if the patient should continue or discontinue trial intervention.

If applicable and if agreed with the Sponsor, visits or specific assessments may be conducted at a patient's home or at a suitable alternative location by mobile qualified and delegated trial personnel. In such cases, the Investigator remains responsible for oversight and protocol procedure adherence. For this purpose, the terms "clinic visit" and "visit to the clinic" in this protocol may also refer to a remote visit.

[figure not shown]

Table 3: Schedule of trial procedures and assessments

	Screening	Double-Blind Treatment Period ^a							
		D1	D8	D29	D85	D141	D169	D267	D365
Procedure/Assessment	W-12 to -1	W1	W2 ^b	W5	W13	W21	W25	W39	W53 ^c
Informed consent	X								
Inclusion/exclusion criteria	X	X ^d							
Demographic data	X								
Medical history including historical liver and kidney ^e volume	X								
Medication/treatment history	X								
Height, BMI	X								
Weight	X	X		X	X		X	X	X
Physical examination	X						X		X
Pregnancy test ^f	X	X ^g			X ^g		X ^g	X ^g	X ^g
Clinical laboratory: hematology, biochemistry, urinalysis, coagulation, thyroid and HbA1c	X ^h	X ^{d,g}		X ^g	X ^g		X ^g	X ^g	X ^g
Serology	X								
Vital signs	X	X ^g			X ⁱ		X ^j	X ^g	X ^g
ECG ^k	X	X ^g			X ⁱ		X ^j	X ^g	X ^g

- a Visit window: ± 1 day for visits with plasma sampling for octreotide measurement and ± 2 days for other visits during the Double-Blind Treatment Period and Extension Period. If the date of a visit does not conform to the schedule, subsequent visits should be planned to maintain the visit schedule relative to the Day 1 visit.
- b Visit may be performed as a phone call.
- c The last dose of IMP in the Double-Blind Treatment Period will be administered in Week 52. The first doses of IMP in the Extension Period will be administered at Week 53 after the last assessments of the Double-Blind Treatment Period have been completed.
- d The Investigator will confirm the patient's eligibility prior randomization on Day 1 based on the data available at the same visit.

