7.6.1.2 Eliciting, Documenting and Reporting of Adverse Events

The Investigator is responsible for ensuring that all AEs and SAEs are recorded on the AE page of the eCRF and reported to the Sponsor (see [Section 7.6.1.3](#) for reporting of SAEs). AEs will be

assessed from the time of signing the ICF until completion of all trial procedures and discharge from the trial. This includes any new event, sign or symptom occurring in the period between screening (after signing the ICF) and the first IMP administration on Day 1. If there is any doubt as to whether a clinical observation is an AE, the event should be reported.

Abnormal laboratory values shall be recorded as AEs if assessed as clinically significant by the Investigator. Laboratory abnormalities that are associated with an already reported medical condition will not be reported as separate AEs but will be used to assess the associated medical condition (e.g., increased neutrophil levels in case of reported infection or increased glucose in a patient with diabetes).

At every visit, patients will be asked a standard question to elicit any medically related changes in their well-being. They will also be asked if they have been hospitalized, have had any accidents, have used any new medications, or have changed concomitant medication regimens (both prescription and over-the-counter medications).

Information to be collected includes trial treatment, type of event, time of onset, dosage, Investigator-specified assessment of seriousness, severity and relationship to trial treatment, and time of event resolution, as well as any required treatment or evaluations, and outcome. AEs resulting from concurrent illnesses, reactions to concurrent illnesses, reactions to concurrent medications, or progression of disease states must also be reported. All AEs should be followed until they have reached a final outcome or the patient's participation in the trial ends, whichever comes first (see further details in [Section 7.6.1.7](#)).

The MedDRA will be used to code all AEs.

Any medical condition that is present at the time that the patient is screened but does not deteriorate thereafter should not be reported as an AE. However, if it deteriorates at any time during the trial, it should be recorded as an AE.

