8.11 Safety Endpoints and Analyses

8.11.1 Adverse Events

Summary tables for AEs will include only AEs that started or worsened after the first administration of IMP, i.e., TEAEs. An overview of all TEAEs including severity, relationship to the IMP, SAEs and TEAEs leading to IMP discontinuation, trial withdrawal or death will be presented by treatment arm and trial period.

TEAEs will be summarized by treatment arm and trial period, system organ class and preferred term (according to MedDRA) displaying number of patients in the treatment arm, number and

percentage of patients having the TEAE as well as the number of TEAEs. Furthermore, TEAEs will be summarized according to severity, relationship, outcome, and seriousness.

SAEs, AESIs, and TEAEs leading to IMP discontinuation or trial withdrawal will be listed and tabulated, if appropriate.

All AEs, deaths and SAEs will be listed and those collected during the pre-treatment period will be flagged.

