5.8 Extent of Exposure and Treatment Compliance

5.8.1 Extent of Exposure

Exposure to CAM2029 or placebo will be summarized using the following parameters based on the data collected in the EDC system in the double-blind treatment period:

- Treatment duration (in weeks), calculated as the number of weeks the patient received IMP: (date of last dose of IMP within each trial period - date of first dose of IMP + 5 half-lives (i.e., 53 days))/7.
- Total number of injections taken, as documented in the patient diary and the eCRF.

The duration of exposure in weeks will be summarized by treatment arm (including the combined active treatment groups) and overall using descriptive statistics for the safety analysis set. The number and percentage of patients with a cumulative duration of exposure will be presented for the following periods: ≥ 4 weeks, ≥ 8 weeks, ≥ 12 weeks, ≥ 24 weeks, ≥ 36 weeks, and ≥ 52 weeks.

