5.10.1 Adverse Events

AEs will be coded using MedDRA version 25.0 (or higher version if updated during the trial or in relation to DBL and agreed with the Sponsor), associating lowest level terms (LLTs) with PTs and SOC by the primary hierarchy. TEAEs are defined as AEs that started or worsened after the first administration of IMP and to the EOT visit or start of another SRL treatment, whichever comes first. Furthermore, the onset date of an TEAE should be prior to the date of last dose of IMP + 5 half-lives (5x10.6 days).

TEAEs, presented as SOC and PTs, will be further defined:

- Treatment period TEAEs are defined as:
 - For patients enrolled into the extension period: TEAEs that occur or worsen on or after the date of first IMP administration in the treatment period and before the date of the first IMP administration in extension period.
 - For patients early terminated from the IMP in the treatment period: all TEAEs reported are double-blind treatment period TEAEs.

The severity of all AEs will be graded using the latest version of the National Cancer Institute Common Terminology Criteria for Adverse Events (CTCAE). Missing severity will be summarized as a separate category.

IMP-related TEAEs are assessed as “Probably related” and “Possibly related”. If the causal relationship to the IMP is missing, the event will conservatively be assigned as related to IMP.

TEAEs of special interest (TEAESI) will be defined pre-DBL as applicable.

An overall AE summary will be presented using the number and percent of patients, and number of events with the following:

- Any AE
- Any TEAE
- Any IMP-related TEAE, including events assessed as “Probably related” and “Possibly related”, or missing relationship to the IMP on the eCRF
- Any TEAE by CTCAE Grade
- Any IMP-related TEAE of CTCAE Grade ≥ 3
- Any TESAE
- Any IMP-related serious TEAE
- Any TEAEs leading to withdrawal from the trial
- Any TEAE leading to IMP discontinuation, including events with action taken with trial treatment = “Drug withdrawn” on the eCRF and TEAEs leading to withdrawal from the trial

- Any TEAE leading to death, including events with outcome = fatal on the eCRF
- Any TEAESI
- TEAESIs of CTCAE Grade ≥ 3
- Any injection site TEAE
- Any related non-injection site TEAESIs
- Any TEAE related to COVID-19

TEAEs will be summarized by trial period, SOC, and PT, with the number and percentage of patients and the number of events, where applicable.

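### The SAP's treatment-emergent window is shorter than the protocol's, so late adverse events in patients who stop IMP but stay in the trial are missing from the detailed AE tables

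*SAP*

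**What the plan says.** Incidence of AEs is a declared secondary endpoint (Protocol Section 3, Table 1; SAP 2.1, Table 3). The two documents define the counted events differently.

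- **Protocol 8.11.1:** "Summary tables for AEs will include only AEs that started or worsened after the first administration of IMP, i.e., TEAEs". There is a start and no end.
- **SAP 5.10.1:** the same start, but the window runs "to the EOT visit or start of another SRL treatment, whichever comes first". In addition, "the onset date of an TEAE should be prior to the date of last dose of IMP + 5 half-lives (5x10.6 days".
- **SAP 5.8.1:** treatment duration is credited to the last dose plus "5 half-lives (i.e., 53 days", with no cut when another SRL starts.

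Follow-up does not end with IMP. Protocol 6.10.1 says "Patients who discontinue IMP treatment during the Double-Blind Treatment Period should NOT be considered withdrawn from the trial", and then "They should return for the assessments indicated in Table 3, up to Week 53". Under Protocol 7.6.1.2, AEs are "assessed from the time of signing the ICF until completion of all trial procedures and discharge from the trial".

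The safety set keeps every dosed patient (SAP 4.7), and percentages use the analysis-set N unless stated otherwise (SAP 5.1). In SAP 5.10.1 the SOC/PT tables and the overview rows for grade, relatedness, seriousness, death and special interest count TEAEs only. The exception is the *Any AE* row. Non-TEAEs are listed separately.

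**The concern.** A patient who stops IMP and stays in the trial can have an AE that the protocol's rule counts and the SAP's rule does not. The patient remains in the denominator while the event leaves the numerator of every detailed summary. Efficacy is handled differently: if such a patient starts no other SRL and has no liver-reducing intervention, liver volume is used to Week 53 under a treatment policy strategy (Protocol 8.9.2).

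Two of the SAP's limits raise further problems. The SRL stop applies even inside the 53 days that SAP 5.8.1 still credits as exposure. The EOT visit has no clear meaning for these patients. The protocol places it at Week 173, at discontinuation during the extension, or at withdrawal of consent (4.1.3, 6.10.2). None of these fits someone who stops IMP in the double-blind period and stays in, so the programmer would have to choose a date.

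What is at stake is the completeness of the by-arm description of harms in a trial with about 23 patients per arm. Some AESIs, such as liver and renal cyst infection, may reflect the underlying disease (Protocol 7.6.1.1), so a drug-washout window is not an obvious boundary for them.

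**Working it through.** **The plan's own figure.** SAP 5.10.1 gives 5 half-lives of 10.6 days: 5 × 10.6 = 53.0 days. This matches SAP 5.8.1.

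**Inputs.** Dosing is weekly from Day 1, so a last dose in Week w falls on Day L = 1 + 7(w − 1). "The last dose of IMP in the Double-Blind Treatment Period will be administered in Week 52", which is Day 358. Week 53 is Day 365 (Protocol Table 3). Onset must be before L + 53, so the last countable day is L + 52.

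**Follow-up excluded, with no other SRL started:** max(0, 365 − (L + 52)).

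| Last dose | L | Last countable day | Days excluded of 365 |
|---|---|---|---|
| Week 1 | 1 | 53 | 312 (85%) |
| Week 5 | 29 | 81 | 284 (78%) |
| Week 13 | 85 | 137 | 228 (62%) |
| Week 25 | 169 | 221 | 144 (39%) |
| Week 39 | 267 | 319 | 46 (13%) |
| Week 45 | 309 | 361 | 4 (1%) |
| Week 46 or later | ≥316 | 365 | 0 |

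Under the protocol's rule the excluded follow-up is 0 days in every row.

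**Scale for an arm (assumption).** Let the last dose of those who stop be uniform over Weeks 1 to 51, with all of them followed to Week 53. Weeks 1 to 45 lose 312, 305, …, 4 days, which sum to 45 × (312 + 4)/2 = 7,110. The mean is 7,110/51 = 139.4 days, and 139.4/365 = 38.2%. The share of the arm's follow-up left uncounted is the stopping proportion × 38.2%:

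- 10% stopping: 3.8%
- 15% stopping: 5.7%
- 30% stopping: 11.5%

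**One patient.** With 69/3 = 23 per arm, one patient with an uncounted event changes an arm's incidence by 1/23 = 4.3 percentage points, or the pooled CAM2029 incidence by 1/46 = 2.2 points.

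**SRL stop against the exposure rule.** Suppose another SRL starts 7 days after the last dose. SAP 5.8.1 still credits 53 days, but TEAE counting ends at day 7. That leaves 53 − 7 = 46 days credited as treatment with no TEAE counted.

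**The early-termination bullet.** SAP 5.10.1 says that for patients who end IMP early, all TEAEs belong to the double-blind period. This assigns events that already qualify as TEAEs to a period. It does not widen the window.

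**The case against.** A five-half-life window is a common and coherent definition of treatment-emergent, and Protocol 8.1 lets the SAP amend the planned analyses. SAP 5.15, on changes to protocol-planned analyses, is not legible in the public text. A reader might infer that the change is undeclared; the documents do not allow that conclusion.

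A reader might also infer that every event after stopping disappears from the safety tables. It does not. Events within 53 days of the last dose count if no other SRL has started. Late events stay in the *Any AE* row, which SAP 5.1 has shown by treatment group, and in the listing. AEs that lead to stopping IMP begin before or around the last dose and are largely unaffected. Laboratory, vital-sign and ECG summaries are not defined by the TEAE window.

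The SRL stop has a rationale. Another SRL can cause the same gastrointestinal, gallbladder and glucose events, and in a placebo patient these would appear as placebo events.

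The expected effect on a single preferred term is also small. Take hypothetical stopping rates of 20% on CAM2029 and 5% on placebo, uniform stopping over 364 days, and a term with 10% annual incidence at constant hazard. The expected loss is 0.33 of a patient in 46 (0.7 points) and 0.04 in 23 (0.2 points), a difference of about 0.5 points.

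All of this stands, and it argues against discarding the on-treatment table. It does not supply what is missing. The *Any AE* row mixes in pre-treatment AEs and has no SOC/PT, grade or seriousness split, and a listing is not a comparison.

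**Conclusion.** The point holds as a mismatch of definitions with a gap in the planned tables. The 53-day limit removes part of the follow-up for any patient whose last double-blind dose is in Week 45 or earlier, by up to 312 of 365 days. Starting another SRL can close the window sooner. The figure of about 4% to 11% of an arm's follow-up rests on two assumptions: 10% to 30% stop IMP, and stopping times are uniform. The documents give no IMP stopping rate. The 15% drop-out in the sample-size section is not one, because patients who leave the trial have no later follow-up to lose.

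It is tempting to conclude that the rule favours CAM2029. The documents do not support that. If CAM2029 is stopped more often, CAM2029 loses more events; if placebo patients start another SRL more often, placebo loses more. Neither rate is given. Nor is a formal randomised comparison broken: safety is descriptive, and the safety set groups patients by treatment received. The case for change is that events already collected would otherwise be missing from the breakdowns by term, grade, seriousness, death and special interest.

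**What to change.** In SAP 5.10.1:

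1. Keep the 53-day TEAE tables and label them on-treatment.
2. Add by-arm tables of all AEs by SOC and PT, SAEs, deaths and AESIs, from the first IMP dose to Week 53 or to the first extension dose. Include events after the start of another SRL and flag them, so that the attribution question stays visible.
3. Reconcile the TEAE definition with Protocol 8.11.1, and state which definition serves the secondary endpoint.
4. State which date replaces the EOT visit for a patient who stops IMP in the double-blind period and stays in the trial.
5. Either align the SRL stop with the exposure rule in SAP 5.8.1 or explain why they differ.

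The cost is SAP wording and one extra set of tables from data already collected. The downside is that some late off-drug or post-SRL events appear in the added tables; setting these beside the on-treatment tables shows how much difference they make.

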5.10.2 Laboratory Evaluations

The following summaries will be generated separately for hematology, biochemistry, coagulation, thyroid, HbA1c and urinalysis tests by treatment group. All laboratory values will be presented in standard international units.

- Summary table of observed values and change from baseline at each assessed visit during the treatment period.

For summary statistics, numerical laboratory measurements values below the lower limit of detection or above the upper detection limit will be replaced by the detection limit reported by the laboratory. In the listings, values will be reported as originally recorded, and in SI units.

In addition to the summary tables above, box plots of observed laboratory test results will be presented.

Laboratory tests for which NCI CTCAE toxicity grading is available will be tabulated separately. For laboratory tests where grades are not defined by CTCAE, results will be categorized by abnormality grades (e.g. low clinically significant/low not clinically significant/normal/high not clinically significant/high clinically significant/missing) based on reference normal ranges. Both the CTCAE grades and abnormality grades will be provided by the central lab.

For laboratory tests where grades are defined by CTCAE, the following tables will be used. Note, lab tests with bi-directional toxicity grades (e.g. hemoglobin decreased [anemia] vs hemoglobin increased) available will be summarized separately under each direction.

- Summary of worst post-baseline CTCAE grade (regardless of the baseline status) during the treatment period. Each patient will be counted only once for the worst grade observed post-baseline while on treatment with IMP.
- Shift from baseline to Week 53 and to the worst post-baseline CTCAE grade during the treatment period.

For laboratory tests where grades are not defined by CTCAE:

- Shift from baseline in abnormality grades to Week 53.
- Shift from baseline in abnormality grades to worst post-baseline value during the treatment period. Where worst value is defined as the value farthest from the normal limit.

In addition, a summary of abnormal laboratory results by visit will be presented by the number and percent of patients in each treatment groups with the following:

- Alanine Transaminase (ALT) > 8x Upper limit normal (ULN)
- Aspartate Aminotransferase (AST) > 8x ULN
- ALT > 5x ULN
- AST > 5x ULN
- Alkaline Phosphatase (ALP) > 2x increase from baseline
- Hemoglobin A1c $\geq 10\%$
- Potassium < 3.5 mmol/L
- Magnesium < 0.7 mmol/L

All laboratory results will be presented in data listings. A separate listing with laboratory test results outside of normal range will also be present.

5.10.3 Vital Signs

Weight, and vital sign results (pulse rate, respiratory rate, body temperature, systolic blood pressure [SBP], diastolic blood pressure [DBP]), and change from baseline values will be presented in data listings by treatment group and patient. Abnormal findings will be flagged (abnormal not clinically significant/abnormal clinically significant).

Weight, and vital sign results will be summarized descriptively using observed values and changes from baseline by treatment group and each visit/at scheduled timepoint for the safety analysis set (SAF).

Box plots of weight and vital sign results will be presented by treatment group and visits for the safety analysis set (SAF).

5.10.4 Electrocardiogram (ECG)

The 12-Lead ECG will be collected in triplicate. The average value of the triplicates at each time point will be used in summaries described below.

ECG parameters (PR, QRS, QT, QTc corrected by Fridericia's formula [QTcF], and RR intervals) will be summarized descriptively using observed values and change from baseline by treatment groups and scheduled visits/timepoints.

Categorical analysis of QT/QTc interval data based on the number and percentage of patients meeting or exceeding predefined limits in terms of absolute QT/QTc intervals or changes from baseline will be presented by treatment arm at each scheduled assessment time point. Categorical analysis of QTcF data will be presented using the boundaries in [Table 7](#).

Table 7: QTcF interval boundaries

QTcF Interval	Criteria (ms)
Observed QTcF interval	≤ 450 msec > 450 to ≤ 480 > 480 to ≤ 500 > 500
Change from baseline in QTcF interval	≤ 30 > 30 to ≤ 60 > 60

In addition, shift from baseline of investigator's overall ECG evaluation (i.e., normal, abnormal not clinically significant, abnormal clinically significant) at each post-baseline visit will be summarized using counts and percentages of patients.

All ECG results and overall ECG evaluation will be presented in data listings by treatment group and patient. Abnormal values will be flagged and categorized as 'abnormal not clinically significant' or 'abnormal clinically significant'.

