7.6.6 Electrocardiogram

ECGs will be recorded and readings will be transmitted to a selected ECG central laboratory for analysis. Triplicate 12-lead ECG (3 ECG recordings at approximately 2-minute intervals) will be performed at each scheduled time point. The combined QTcF values from triplicate ECGs will be averaged to provide a single value for each patient. ECGs will be recorded at screening and at the time points outlined in [Table 3](#).

ECGs will be recorded after the patient has been resting in a supine position for at least 10 minutes. All ECGs should be recorded with the patient in the same physical position. ECGs will be recorded after vital signs and before blood samples for PK and clinical safety laboratory assessments.

The ECG assessments pre-dose and at the 24-hour time point have been selected to coincide with trough concentrations and near C_{max} of octreotide for CAM2029, based on PK results from trial HS-11-411. If at any visit QTcF ≥ 481 msec is observed, the procedures for QT-prolongation management described in [Section 17.1.2](#), Appendix 1 must be considered.

All ECG assessments will initially be assessed by the Investigator/qualified physician for any findings that require immediate medical attention. All ECGs will also be read by an ECG central reader. The clinical significance of any ECG findings will be determined by the Investigator, including after the central reading result is available. However, only ECG results provided by the central reader will be recorded in the clinical database.

Clinically significant abnormalities that are known at the time of signing the ICF should be reported on the Medical History eCRF page. Clinically significant findings must be discussed with the Sponsor before enrolling the patient in the trial. New or worsened clinically significant findings occurring after signing of the ICF must be recorded on the AE page of the eCRF.

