8.11.4 Electrocardiogram

Triplicate 12-lead ECGs including PR, QRS, QT, QTcF and RR intervals will be obtained for each patient during the trial. Data will be listed and summarized descriptively.

Categorical analysis of QT/QTc interval data based on the number of patients meeting or exceeding predefined limits in terms of absolute QT/QTc intervals or changes from baseline will be presented. In addition, a listing of these subjects/patients will be produced.

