17.1.2 Specific Management Recommendations for Cases of QTcF Prolongation

Table 5: Dose interruptions for QTcF prolongation

Severity	Dose adjustment and management recommendation
For all grades	
Check the quality of the ECG and the QT value and repeat if needed. Analyze serum electrolytes (potassium, calcium, phosphorus, magnesium). If electrolytes are significantly outside of normal range, correct with supplements or appropriate therapy as soon as possible, and repeat electrolyte analyses until documented as normal.
 
Review concomitant medication usage for the potential to prolong the QT interval.
 
Check compliance with correct dose and administration of IMP.
 
Consider collecting a time-matched PK sample; record date and time of last IMP intake.

Grade 1
 
Average QTcF: Males: 450 msec to 480 msec Females: 470 msec to 480 msec
	No dose interruption recommended.

Grade 2
 
Average QTcF: 481 msec to 500 msec
	
Pause IMP.
 
Perform repeated triplicate ECGs approximately 1 hour after the first QTcF of ≥ 481 msec.
 
If QTcF < 481 msec, restart IMP.
 
If QTcF remains ≥ 481 msec, repeat ECG as clinically indicated until the QTcF returns to < 481 msec. Restart IMP.
 
If QTcF ≥ 481 msec remains or recurs, consider discontinuing IMP.
 
Repeat ECGs 7 days and 14 days after dose resumption (then as clinically indicated) for any patient who had therapy interrupted due to QTcF ≥ 481 msec.

Grade 3
 
Average QTcF: ≥ 501 msec or > 60 msec change from baseline
 
or
 
Grade 4
 
Torsades de pointes or polymorphic ventricular tachycardia, or signs/symptoms of serious arrhythmia
	
Perform repeated triplicate ECGs within 1 hour of the first QTcF of ≥ 501 msec or > 60 msec change from baseline.
 
If QTcF remains ≥ 501 msec or if the change from baseline remains > 60 msec, discontinue IMP.
 
Transmit ECG immediately and confirm prolongation/abnormalities with central assessment.
 
Obtain local cardiologist (or qualified specialist) consultation and repeat cardiac monitoring as indicated until the QTcF returns to ≤ 500 msec.
 
Repeat ECG as clinically indicated until the QTcF returns to < 481 msec.

ECG: electrocardiogram; IMP: investigational medicinal product; PK: pharmacokinetic; QTcF: QTc interval corrected by Fridericia's formula

SPONSOR PROTOCOL SIGNATURE PAGE

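### The SAP tabulates QTcF categories by scheduled time point only and states no per-patient worst post-baseline summary, so the by-arm table may miss off-schedule exceedances and gives no count of patients who ever exceeded a limit

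*SAP*

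**What the plan says.** SAP 5.10.4 plans numbers and percentages of patients in QT/QTc categories. It states that absolute values and "changes from baseline will be presented by treatment arm at each scheduled assessment time point". The next sentence refers to Table 7 for the QTcF boundaries (observed values above 450, 480 and 500 msec; increases above 30 and 60 msec) and gives no time basis of its own. The section mentions neither a maximum post-baseline value nor a count of patients above a limit at any time.

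Protocol 8.11.4 describes a categorical analysis "based on the number of patients meeting or exceeding predefined limits in terms of absolute QT/QTc intervals", or changes from baseline, with no restriction to scheduled visits. It then adds: "In addition, a listing of these subjects/patients will be produced". SAP 5.10.4 does not repeat that outlier listing. It does state: "All ECG results and overall ECG evaluation will be presented in data listings by treatment group and patient". Values in that listing are flagged by clinical significance, not by Table 7 limit.

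Protocol 7.6.6 says that, for a QTcF of 481 msec or more at any visit, the QT procedures in "Appendix 1 must be considered". Those procedures (protocol 17.1.2, Table 5) include repeat triplicates about 1 hour after a value of 481 msec or more, and within 1 hour after a value of 501 msec or more or a change above 60 msec. After an interruption for a value of 481 msec or more they add: "Repeat ECGs 7 days and 14 days after dose resumption". Under protocol 6.10.1 the QT discontinuation criterion is judged after the repeated triplicate, with central confirmation.

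**The concern.** QT prolongation is a named group of adverse events of special interest (protocol 7.6.1.1) and has its own discontinuation criteria. The ECGs that confirm or extend a prolongation are mostly off schedule, while the by-arm table is tied to the schedule. The table could therefore place a patient in a lower category than the patient reached, or miss a patient whose exceedance was seen only off schedule.

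Even with scheduled ECGs alone, a reader of the table cannot tell whether exceedances at several time points come from one patient or from several. The number of patients per arm who ever exceeded a limit is the usual summary for this risk, and it is what the protocol's wording suggests. The SAP already takes this approach for laboratory tests: section 5.10.2 counts each patient once at the worst post-baseline CTCAE grade. Section 5.2.1 also expressly admits unscheduled visits when it defines baseline.

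**Working it through.** The plan states no figure on this point, so there is nothing to reproduce. The check has two parts: a comparison of the texts, and an illustration of what rows by time point can and cannot show.

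**1. Which ECGs have a place in the table.** Protocol Table 3 gives six scheduled post-baseline ECG time points in the double-blind period: Week 13 pre-dose and about 24 hours post-dose, Week 25 pre-dose and about 24 hours post-dose, Week 39 pre-dose and Week 53 pre-dose. Four are therefore pre-dose. Protocol 7.6.6 associates pre-dose ECGs with trough concentrations and the 24-hour ECG with concentrations near the maximum.

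Taking the SAP sentence as written, the cases are:

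- *Scheduled value exceeds a limit; the repeat is in the same or a lower category.* The first value is already in that visit's row. Nothing is lost there, and later normal values do not erase the row.
- *Scheduled value of 481 to 500 msec; the repeat is 501 msec or more.* The scheduled row keeps the patient in the category above 480 up to 500 msec. The value above 500 msec has no stated row, although it bears on discontinuation.
- *ECGs 7 and 14 days after resumption.* These patients have already had a value of 481 msec or more. What can be missed is a first move above 500 msec or above a 60 msec increase.
- *First exceedance on an ECG done off schedule for clinical reasons.* No scheduled row receives it.

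**2. What the rows add up to.** Let p be the proportion of patients above a limit at each time point. No document gives p, so it is an assumption. With 69 / 3 = 23 patients per arm and k = 6 time points:

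- expected patients in each row = 23 × p;
- expected patients ever above the limit, if the same patients exceed it every time = 23 × p;
- expected patients ever above the limit, if time points are independent = 23 × [1 − (1 − p)^6].

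| Assumed p | Each row | Ever, same patients | Ever, independent |
|---|---|---|---|
| 1% | 0.23 | 0.23 | 1.35 (5.9%) |
| 2% | 0.46 | 0.46 | 2.63 (11.4%) |
| 5% | 1.15 | 1.15 | 6.09 (26.5%) |

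For p = 5%: 1 − 0.95^6 = 0.265, and 23 × 0.265 = 6.1. In general the ever-exceeded count lies between the largest single row and the sum of the six rows, here 6 × 1.15 = 6.9. The rows do not say where in that range it falls.

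This illustration concerns scheduled time points only. It does not measure what is lost by leaving out unscheduled ECGs, and the documents give no rate from which that could be estimated.

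**The case against.** The strongest reply is that the patients in question remain visible. The protocol promises a listing of those who exceed limits, and the SAP lists all ECG results by patient without restricting them to scheduled ECGs. Protocol 7.6.6 requires new or worsened clinically significant ECG findings to be recorded as adverse events. SAP 5.10.1 then counts patients with any treatment-emergent event of special interest, with such events of Grade 3 or higher, and with events leading to IMP discontinuation. All of this stands. A reader might infer that the number of patients who ever exceeded a limit is never reported. The documents do not support that: the number can be counted by hand from the listings. What is missing is a stated summary by arm.

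A reader might also infer that unscheduled ECGs are excluded from Table 7. No sentence says so. The Table 7 sentence has no time basis, the analysis visit window section (SAP 5.2.3) has no visible text in the public copy, and the table shells are in a separate document. It can be said only that these ECGs have no stated place.

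Nor are the off-schedule ECGs strictly mandatory. Protocol 17.1.2 is headed as recommendations, the procedures are to be considered, and several ECGs depend on clinical indication.

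Finally, a reader might conclude that arrhythmia risk will be understated. That is not shown. It would require an exceedance seen only off schedule or a repeat in a higher category, and the lower end of the illustration is no difference at all.

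**Conclusion.** The point holds as a modest reporting gap. On the visible text, the SAP's categorical QT/QTc summary is narrower than the one in protocol 8.11.4. It has no per-patient worst value, gives off-schedule ECGs no stated place, and does not repeat the protocol's outlier listing. The by-arm summary may therefore omit some exceedances and cannot yield the number of patients who ever exceeded a limit.

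The size cannot be fixed from the documents. Under an assumed 5% per time point in arms of 23, the ever-exceeded count would be about 1 if the same patients recur and about 6 under independence. Positive correlation within patients would put it between these.

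The conclusion rests on reading the SAP sentence as written. It would weaken if the visit-window rules or the table shells already bring in unscheduled ECGs or a maximum-value row. The safety analyses are descriptive, so no test, significance level, sample size or primary result is affected. This is an inexpensive improvement, not a flaw that threatens the trial.

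**What to change.** Add to SAP 5.10.4 one table by arm that applies the Table 7 categories to each patient's maximum post-baseline QTcF and maximum change from baseline, counting each patient once.

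- **Data:** all centrally read ECGs, scheduled and unscheduled, including repeat triplicates, with each triplicate averaged as already planned.
- **Window:** the SAP's own treatment-emergent window in 5.10.1, that is, from first IMP to the earliest of the EOT visit, the start of another SRL, or last dose plus 5 × 10.6 = 53 days. ECGs should also precede the first extension dose. State this last cut-off by time rather than date, because the Week 53 ECG is taken pre-dose on the day of that dose and should be kept.
- **Keep** the rows by scheduled time point, and say whether unscheduled ECGs enter them.
- **Carry over** the protocol's listing of patients exceeding limits, with a flag by Table 7 limit.

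The cost is one table and one listing. Protocol 7.6.6 has all ECGs read centrally, and SAP 5.1.1 already provides for the central ECG transfer. The downside is that patients examined more often have more chances to exceed a limit, which slightly raises their counts. A footnote with the number of patients per arm who have unscheduled ECGs would let the reader judge this. No clinical rule changes.
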